12.4.4 Sensitivity Analyses of the Key Secondary Endpoints

For the two key secondary endpoints, 50% response (Weeks 1-12) and 75% response (Weeks 1-12), a sensitivity analysis will be performed, where any patient that does not have a value of MMDs for all 3 post-baseline 4-week periods included in Weeks 1-12 will be imputed with a non-response.

For the key secondary endpoint, change from baseline in the number of MMDs (Weeks 13-24), a sensitivity analysis will be conducted similarly to the one described for the primary endpoint under *Imputation for Weeks 1-4* (Section 12.3.5), i.e. where monthly values in the first 4 weeks after first infusion are calculated using the *weighting* rule described in Section 19.1.1.1 if patients have less than 14 days with eDiary reporting in this period.

For the key secondary endpoint, change from baseline in HIT-6 total score, a sensitivity analysis using the placebo-based multiple imputation method to assess the robustness of the conclusions for this endpoint to the type of missing data will be conducted.

An analysis will be performed using a pattern-mixture model (PMM), in which missing HIT-6 total scores will be imputed using a sequential regression-based multiple imputation method, based on the imputation models established from the placebo group.⁴

200 simulations will be performed to generate the datasets that will be analysed using the model described in section 12.4.2. These analyses will be combined using Rubin's rule to form a unique point estimate and standard error, taking into account the uncertainty of the imputation.⁵ The SAS[®] code for this sensitivity analysis is shown in Appendix IV.

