4.5.2 Headache Day

A headache day is defined as any day with a headache that meets one of the following criteria:

- Lasted 30 minutes or more
- Meets the criteria for being a migraine, i.e. fulfils either criteria A, B, C or D above (see Section 4.5.1)

5 Analysis Sets

The following analysis sets will be used to analyse and present the data:

- all-patients-randomized set (APRS) all randomized patients
- *all-patients-treated set* (APTS) all patients in the APRS who received at least one infusion of the double-blind IMP
- *full-analysis set* (FAS) all patients in the APTS who had a valid baseline assessment and at least one valid post-baseline 4-week assessment of MMDs in Weeks 1-12
- *all-patients-treated-long-term* set (APTS_LT) all patients in the APRS who received at least one infusion of IMP and had a visit in the Extension Period
- *full-analysis-long-term set* (FAS_LT) all patients in the APTS_LT who had a valid baseline assessment and a valid assessment of monthly migraine days in the Extension Period

The patients and data will be classified into the analysis sets according to these definitions at separate *Classification Meetings*:

- For the reporting of the Placebo-controlled Period, the Classification meeting will be held after the data base release for the reporting of the Placebo-controlled Period but before the blind has been broken and will concern the classification into APTS and FAS.
- For the *addendum to CSR*, the Classification meeting will be held after the data base release for the reporting of the Extension Period and will concern the classification into APTS_LT and FAS_LT.

Efficacy analyses of the Placebo-controlled Period will be based on FAS, and efficacy analyses in the Extension Period will be based on FAS_LT.

Safety tables (including exposure and concomitant medications) will be based on APTS in the Placebo-controlled Period and APTS_LT in the Extension Period.

6 Descriptive Statistics

Unless otherwise specified, summary statistics (n, arithmetic mean, standard deviation [SD], median, lower and upper quartiles, minimum and maximum values) will be presented for continuous variables, and counts and, if relevant, percentages will be presented for categorical variables.

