12.1 General Efficacy Analysis Methodology

Unless otherwise specified, all the efficacy analyses for the Placebo-controlled Period will be based on the FAS and all the efficacy analyses for the Extension Period will be based on the FAS_LT.

All the tables and graphs will be presented by treatment group for the Placebo-controlled Period and both by treatment group and treatment sequence group for the Extension Period.

All the p-values will be based on two-sided tests; the confidence intervals (CIs) will be twosided; and the endpoints not included in the testing strategy will be presented with nominal pvalues and 95% CIs.

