For patients with any post-baseline suicidal ideation or behaviour in the Placebo-controlled Period (C-SSRS scores of 1 to 10), listings will be provided based on APRS including all C-SSRS scores prior to entering the Extension Period for those patients for inclusion in the *CSR*.

A similar listing will be provided for patients with any post-baseline suicidal ideation or behaviour in the Extension Period including all the C-SSRS scores for those patients for inclusion in the *addendum to CSR*.

14 Blinded Data Reviews

The quality of the study will be overseen by performing blinded data reviews during the conduct of the study. The reviews may include, but are not limited to, data quality, protocol adherence, and the appropriateness of design assumptions, including the sample size assumptions.

An independent Safety Data Monitoring Committee (DMC) will regularly monitor the patients' safety data according to the *DMC Charter*. The DMC will have access to unblinded information for the double-blind treatment for each patient. Members of the DMC will not be involved in other study-related tasks.

15 Interim Analyses

See Section 18.

16 Sample Size Considerations

The two prior eptinezumab Phase III studies, PROMISE-1 performed in an EM population and PROMISE-2 performed in a CM population, had the following effect sizes for the primary endpoint when compared to placebo (standard deviations):

- EM: 100 mg 0.69 (3.1), 300 mg 1.11 (3.1)
- CM: 100 mg 2.03 (5.8), 300 mg 2.60 (5.8)

The power was determined by simulating the testing strategy (10000 simulations) assuming normal distributions with similar mean and SD for continuous endpoints and similar success rates as the response variables in the Phase III studies for the corresponding population (EM or CM) without assuming the variables to be correlated. With 280 patients per treatment group, assuming that 40% of the patients will be from the EM population and 60% from the

CM population, and that 2% of the patients not having a post-baseline assessment of the primary endpoint, simulations show that the power for the test of the primary endpoint is approximately 94% for the comparison of 100 mg to placebo and 99% power for the comparison of 300 mg to placebo. The individual key secondary endpoints had a power of at least 68% for showing an effect, with a combined power of 58% for seeing an effect for all primary and key secondary endpoints and both doses in the testing strategy.

17 Statistical Software

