19.1.1.1 Monthly Migraine Days (MMDs)/Monthly Headache Days (MHDs)

The following describes the derivation of MMDs. The derivation of MHDs follows the same principles.

4-Week Intervals

For Baseline and each 4-week period post-baseline in the study, the number of MMDs will be derived as the number of migraine days within each 28-day interval using the imputation rules described below. The 4-week periods post-baseline that are considered are the following: Weeks 1-4, Weeks 5-8, Weeks 9-12, Weeks 13-16, Weeks 17-20, Weeks 21-24, Weeks 25-28, Weeks 29-32, Weeks 33-36, Weeks 37-40, Weeks 41-44, Weeks 45-48, Weeks 49-52, Weeks 53-56, Weeks 57-60, Weeks 61-64, Weeks 65-68, Weeks 69-72.

In general, for 4-week periods where the eDiary is completed on at least 14 days out of the 28 days, prorating will be used to calculate the MMDs, and for 4-week periods where the eDiary is completed on less than 14 days out of the 28 days, the MMDs will be set to missing. However, there are cases where weighting will be used when less than 14 days have been completed, and an overview is given in Panel 5.

Prorating

Intended to be used for 4-week periods where the eDiary is completed on at least 14 out of the 28 days, the prorating procedure consists of imputing days with missing information with the observed mean number of migraine days in the period as follows:

28*(Reported Migraine Days/Reported eDiary Days)

This imputation rule will also be used for the Baseline value regardless of the number of reported eDiary days in the screening period. Patients are, however, required to demonstrate compliance with the eDiary and fill it out for at least 24 out of the 28 days in the screening period in order to be eligible for randomization.

Weighting

Intended to be used in special cases for the first 4-week period post-baseline, where the eDiary is completed on less than 14 days out of the 28 days due to withdrawal. When weighting is used, the number of MMDs is derived as a weighted sum of the observed mean number of migraine days in the period and the mean MMDs for the preceding period as follows:

$$28*(W*X + (1 - W)*X_p),$$

where $W = Reported \ eDiary \ Days/13$, $X = Reported \ Migraine \ Days/Reported \ eDiary \ Days$, and $X_p = preceding \ MMDs/28$.

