Patients who withdraw due to lack of efficacy so early that they only have post-baseline data from Weeks 1-4 will have their MMDs calculated using weighting for Weeks 1-4 if they have less than 14 days of eDiary reporting during the first 4 weeks of the study. If they have 14 days or more in this period, their MMDs for Weeks 1-4 will be calculated using prorating.

Patients who withdraw due to adverse events so early that they only have post-baseline data from Weeks 1-4 will have their MMDs calculated using weighting for Weeks 1-4 if they have less than 14 days of eDiary reporting during the first 4 weeks of the study. If they have 14 days or more in this period, their MMDs for Weeks 1-4 will be calculated using prorating.

	Number of Reported eDiary Days		ed eDiary Days in Period
Description	4-Week Period	0-13	14-28
All patients randomized	Baseline	Prorating*	Prorating
Patients not withdrawing due to lack of efficacy/adverse event	Weeks 1-4	None (missing)	Prorating
Patients not withdrawing due to lack of efficacy/adverse event	4-week periods after week 4	None (missing)	Prorating
Patients withdrawing due to lack of efficacy	Weeks 1-4	Weighting	Prorating
Patients withdrawing due to lack of efficacy	4-week periods after week 4	None (missing)	Prorating
Patients withdrawing due to adverse event	Weeks 1-4	Weighting	Prorating
Patients withdrawing due to adverse event	4-week periods after week 4	None (missing)	Prorating

Panel 5 Overview of Imputation Rules for 4-Week Periods for eDiary Data

*Patients are required to complete the eDiary for at least 24 days during the first 28 days of screening to be eligible

In case of a reporting day where a patient answers in the evening diary that they experienced a headache on that day but then never fills out an actual headache in the headache diary, the day will be assigned as a no headache and no migraine day.

When the number of MMDs have been calculated for a given 4-week period, the result will be rounded to two decimals.

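### The non-response sensitivity analysis for the 50% and 75% responders defaults to the FAS, so treated patients with no valid month in Weeks 1-12 are left out instead of counted as non-responders

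*SAP*

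**What the plan says.** - **The rule.** SAP 12.4.4 imputes non-response for "any patient that does not have a value of MMDs for all 3 post-baseline 4-week periods included in Weeks 1-12". The section does not say which analysis set is used. It gives no other sensitivity analysis for these two endpoints.
- **The default set.** SAP 12.1 states that, unless otherwise specified, "all the efficacy analyses for the Placebo-controlled Period will be based on the FAS".
- **Entry to the FAS.** SAP Section 5 requires a valid baseline and "at least one valid post-baseline 4-week assessment of MMDs in Weeks 1-12". The wider APTS is "all patients in the APRS who received at least one infusion of the double-blind IMP".
- **When a month is missing.** Under SAP 19.1.1.1, when "the eDiary is completed on less than 14 days out of the 28 days, the MMDs will be set to missing".
- **Exceptions.** The same section and Panel 5 give a weighted Weeks 1-4 value, even with fewer than 14 diary days, to two groups: "Patients who withdraw due to lack of efficacy so early that they only have post-baseline data from Weeks 1-4" and "Patients who withdraw due to adverse events so early that they only have post-baseline data from Weeks 1-4".
- **Main responder analysis.** SAP 19.1.1.2 derives the 12-week status from whichever months are available.
- **Planning figure.** SAP Section 16 assumes "2% of the patients not having a post-baseline assessment of the primary endpoint", with 280 patients per group.

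**The concern.** The rule is worded to reach any patient with incomplete monthly data, but the default set removes the patients with the least data before the rule is applied. One or two missing months make a patient a non-responder; three missing months take the patient out of the denominator. No responder analysis in the APTS or APRS is planned elsewhere.

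FAS membership depends on diary completion after randomisation. The estimand population in SAP 12.3.1, carried over in 12.4.1, is all patients who meet the selection criteria. A check run only in the FAS shares the main analysis's selection and cannot show whether that selection matters. What is at stake is how informative one supporting analysis is.

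**Working it through.** **1. Who is left out.** The outcome for a treated patient with a valid baseline, under the SAP as written:

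| Weeks 1-12 data | In FAS? | Status in the 12.4.4 analysis |
|---|---|---|
| All three months valid | Yes | By observed change |
| One or two months missing | Yes | Non-responder |
| Withdrew in Weeks 1-4 for lack of efficacy or adverse event, 1-13 diary days | Yes, if a weighted value counts as valid | Non-responder |
| Same, 0 diary days | Unclear | Non-responder or left out |
| No valid month, any other reason | No | Left out |

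The weighting formula is 28 × (W × X + (1 − W) × Xp), with W = diary days/13, X = migraine days/diary days and Xp = preceding MMDs/28. With a baseline of 14 MMDs, so Xp = 0.5:
- 1 diary day, 0 migraine days: 28 × (0 + 12/13 × 0.5) = 12.92, a change of −7.7%.
- 5 diary days, 3 migraine days: 28 × (3/13 + 8/13 × 0.5) = 15.08, a change of +7.7%.
- 13 diary days, 3 migraine days: 28 × 3/13 = 6.46, a change of −53.8%.

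The third patient is a 50% responder in the main analysis. With no later months, the same patient is a non-responder in the sensitivity analysis, so the rule does act on early withdrawals for these two reasons. With 0 diary days, X is 0/0. Panel 5 assigns weighting to 0-13 days, but the text presumes some Weeks 1-4 data.

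**2. The plan's own figure.** Inputs from SAP Section 16: effects (SD) for EM of 0.69 and 1.11 (3.1), for CM of 2.03 and 2.60 (5.8), a 40/60 mix, 280 per arm and 2% without data. The two-sided 5% level is from SAP 12.1 and 12.2.
- n = 280 × 0.98 = 274.4 per arm.
- Mean difference: 0.4 × 0.69 + 0.6 × 2.03 = 1.494 for 100 mg; 0.4 × 1.11 + 0.6 × 2.60 = 2.004 for 300 mg.
- SD = √(0.4 × 3.1² + 0.6 × 5.8²) = 4.902.
- Two-sample power: 94.6% and 99.8%, confirmed by 10,000 simulated t-tests. The plan states about 94% and 99%.

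The stated power is therefore consistent with a simple 2% reduction in sample size.

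**3. How many patients.** 2% of 280 = 5.6 per arm; 2% of 840 = 16.8 in total. This is an upper figure for the APTS at that assumption, because the 2% may include patients never infused.

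**4. Effect on the risk difference.** Let ra and rp be the FAS response rates and ma and mp the shares left out. Counting those patients as non-responders gives ra(1 − ma) − rp(1 − mp). If ma = mp = m, this is (1 − m)(ra − rp), a factor of 0.98 at 2%. The documents give no response rates, so 45% versus 15% is assumed:

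| Left out, active / placebo | Calculation | Difference (FAS 30.0) |
|---|---|---|
| 2% / 2% | 44.1 − 14.7 | 29.4 |
| 3% / 1% | 43.65 − 14.85 | 28.8 |
| 4% / 1% | 43.2 − 14.85 | 28.4 |

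**5. Smaller differences.** These are unadjusted two-proportion power calculations with assumed rates. With equal 2% exclusion, placebo rates of 10-40% and differences of 10-20 points, power changes by less than 1 point. In a stress case with 4% left out on active and none on placebo:
- 45% versus 30%: 15 points becomes 43.2 − 30 = 13.2, and power goes from 95.4% to 90.2%.
- 50% versus 40%: 10 points becomes 48 − 40 = 8.0, and power goes from 65.4% to 47.9%.

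**The case against.** A reader might infer that the clearest treatment failures are dropped. The SAP does not support that: early withdrawals for lack of efficacy or adverse event with some diary data receive a weighted value, can enter the FAS, and are then counted as non-responders. For most of those left out the outcome is unknown, not a known failure. SAP Section 2 also expects withdrawn patients to keep the diary until the Withdrawal Visit, which limits their number. This objection stands.

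A reader might also take the analysis to be offered as a conservative bound. Neither document calls it that. Protocol 16.8.5 gives the aim as assessing the impact of the imputations, and holding the FAS fixed while changing only the missing-month rule isolates that assumption. This is a fair defence of the present design. It does not help with the separate question of whether FAS selection matters, which no planned responder analysis addresses.

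Finally, the patients remain visible in the report. SAP 7.1 gives APTS and FAS counts by group, 7.2 gives withdrawals by reason, and Section 11 gives diary compliance. A reader could recompute a crude difference, but not the covariate-adjusted odds ratio.

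**Conclusion.** The point holds as a cheap improvement. As written, the sensitivity analysis counts treated patients with one or two missing months as non-responders and omits those with none valid. It may also omit early lack-of-efficacy or adverse-event withdrawals with 0 diary days.

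At the planned 2%, equal exclusion moves an assumed 30-point difference by 0.6 points. For a given overall share left out, the shift is larger only if exclusion is higher on active treatment: 1.6 points in the assumed 4%/1% case. The response rates and unequal splits are assumptions. The conclusion also takes a weighted value to be valid for FAS entry, which the SAP does not state.

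Because the 50% and 75% responders appear in the testing sequence, a reader might infer that the formal conclusions are affected. They are not: those steps use the main logistic regression in SAP 12.4.2, and this sensitivity analysis has no role in them.

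**What to change.** In SAP 12.4.4, state that the non-response sensitivity analysis for the 50% and 75% responders is done on the APTS. Every treated patient lacking one or more of the three monthly values, including all three, is counted as a non-responder. Report the number of APTS patients outside the FAS by arm and reason. The main FAS analysis stays as it is.

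The model can be fitted without new data. It needs treatment, stratum and baseline MMDs; Panel 5 prorates baseline for all randomised patients, and eligibility requires 24 of 28 screening diary days. The 0-diary-day ambiguity also stops mattering for this analysis, since such patients lack later months and are non-responders either way.

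The cost is a change of analysis-set filter, one small table, and slightly lower response rates in one sensitivity analysis.

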12.5 Analysis of the Secondary Endpoints

The following endpoints will be derived according to the descriptions given in Section 19.1 and analysed using the same methodology as that described for the primary endpoint (see Section 12.3.2) with a few exceptions, which are highlighted below the list:

- Change from baseline in the number of MHDs (Weeks 1-12)
- Change from baseline in percentage of migraine/headaches with severe pain intensity (Weeks 1- 12)
- Change from baseline in the number of MMDs with use of acute medication (Weeks 1- 12 and Weeks 13-24)
- Change from baseline in the number of monthly days with use of acute migraine medication (Weeks 1-12 and Weeks 13-24)
- PGIC score at Week 12 and at Week 24
- Change from baseline in the number of MMDs in patients with MOH (Weeks 1-12)
- MBS score at Week 12
- Change from baseline to Week 24 in the HIT-6 score

- Change from baseline to Week 12 and to Week 24 in MSQ v2.1 sub-scores (Role Function-Restrictive, Role Function-Preventive, Emotional Function)
- Change from baseline to Week 12 and to Week 24 in EQ-5D-5L VAS score
- Change from baseline to Week 12 and to Week 24 in WPAI sub-scores (Absenteeism, Presenteeism, Work productivity loss, Activity impairment)

For the endpoints listed above, the baseline MMD score will be replaced with the baseline score for the endpoint in question in the model except for analysis of PGIC and MBS, which will exclude the baseline score terms, since the rating of the scales in themselves represent a change from baseline so no baseline score exists.

In the analysis of MHDs, the model will include following fixed effects: month, country, and treatment as factors, baseline MHDs as a continuous covariate, treatment-by-month interaction, and baseline score-by-month interaction.

The analysis of MMDs in patients with MOH will only be performed if the number of patients with MOH constitutes a sufficiently large part of the study population.

For HIT-6, in addition to summary tables presenting descriptive statistics for the total score, tables presenting the counts and percentages of patient in each life impact category as defined in Section 19.1.4 will be produced by visit and treatment group.

The following endpoints will be analysed using the same methodology as that described for the key secondary response endpoints (see Section 12.4.2):

- Response: Patients with 50% reduction from baseline in MMDs (Weeks 13-24)
- Response: Patients with 75% reduction from baseline in MMDs (Weeks 13-24)
- Response: Patients with 50% reduction from baseline in MHDs (Weeks 1-12)
- Response: Patients with 75% reduction from baseline in MHDs (Weeks 1-12)
- Response: Patients with a 5-point reduction from baseline to Week 12 and from baseline to Week 24 in HIT-6

For the HIT-6 response endpoints, LOCF will be used to impute a potentially missing value at Week 12 or Week 24. Baseline values will not be carried forward.

The following endpoints:

- Response: Patients with 100% reduction from baseline in MMDs (Weeks 1-12)
- Response: Patients with 100% reduction from baseline in MHDs (Weeks 1-12)
- Patients with a migraine on the day after first dosing

Will be derived according to the descriptions in Section 19.1.1.2 and 19.1.1.3 and analysed using an extended Cochran-Mantel-Haenszel (CMH) test, adjusting for one of the stratification factors (MHDs at baseline: $\leq 14 /> 14$). The rates for each dose of eptinezumab and placebo will be presented. The SAS[®] code for performing the extended CMH test is shown in Appendix IV.

Descriptive tables displaying the distribution of answers to the items in HCRU at each visit will be provided by treatment group.

Tables displaying the counts and percentage of answers to each category of response options for each item of EQ-5D-5L will be presented by visit and treatment group. Furthermore, shift tables displaying for each item in EQ-5D-5L the number and percentage of patients who decreased, increased or had no change from baseline in the item score will be provided by visit and treatment group.

For inclusion into the *addendum CSR*, the endpoints listed below will be derived according to the descriptions given in Section 19.1 and the absolute values will be analysed using an MMRM similar to the one described for the primary endpoint (see Section 12.3.2) but using treatment sequence group instead of treatment group.

No treatment comparisons will be performed for any of the efficacy endpoints after Week 24. Instead, the estimated mean values will be reported with two-sided 95% confidence intervals by treatment sequence for:

- Number of MMDs (at Weeks 1-4, Weeks 5-8, Weeks 9-12, Weeks 13-16, Weeks 17-20, Weeks 21-24, Weeks 25-36, 37-48, 49-60, and 61-72)
- HIT-6 score (at week 4, 8, 12, 16, 20, 24, 36, 48, 60, and 72)

The absolute values and changes from baseline in MMDs at Weeks 25-36, 37-48, 49-60, and 61-72 will be summarized descriptively by treatment sequence group and by treatment group in the Extension Period.

Similarly, the absolute values and changes from baseline in HIT-6 total score at Weeks 36, 48, 60, and 72 will be summarized descriptively by treatment sequence group and by treatment group in the Extension Period.

Tables displaying the counts and proportion of patients achieving a 50% and 75% reduction from baseline in MMDs across Weeks 25-36, 37-48, 49-60, and 61-72 will be presented by treatment sequence group and by treatment group in the Extension Period.

